To completely inform all participants in this study concerning the pertinent details and purpose of the study prior to their agreement to participate in the study in accordance with GCP and regulatory authority requirements.

To be responsible for maintaining each participant's consent form in a secure study file and providing each participant with a signed copy of the consent form.

That I am thoroughly familiar with the appropriate use of the investigational product(s), as described in the protocol, and any additional information provided to me by, or on behalf of AOBiome LLC.

Investigator Printed Name: _____

Signature: _____ **Date:** _____

Statement of Compliance

The study will be carried out in accordance with Good Clinical Practice (GCP) as required by the following:

United States (US) Code of Federal Regulations (CFR) applicable to clinical studies (45 CFR Part 46; 21 CFR Part 50, 21 CFR Part 56, and 21 CFR Part 312)
ICH E6; 62 Federal Register 25691 (1997)

All key personnel (all individuals responsible for the design and conduct of this study) have completed Good Clinical Practice Training.

CLINICAL TRIAL SYNOPSIS

COMPOUND: B244

STUDY NUMBER: **ARB244-001**

TITLE:	A Prospective, Controlled, Double Blind, Multi-Center, Randomized, 3 arm, Phase 1b/2a Study to Assess the Safety, Tolerability, and Preliminary Efficacy of B244 Delivered as an Intranasal Spray in Healthy Volunteers and Subjects with Seasonal Allergic Rhinitis
INVESTIGATIONAL PRODUCT	B244
STUDY ARMS	B244 (140ul per nostril; OD 0.5; 1×10^9 cells/ml) twice-a-day for 14 days B244 (140ul per nostril; OD 2.0; 4×10^9 cells/ml) twice-a-day for 14 days Vehicle (140ul per nostril) twice-a-day for 14 days
PURPOSE:	To assess the safety and tolerability of B244 relative to Vehicle in healthy volunteers and to evaluate the preliminary efficacy of B244 relative to Vehicle in subjects with seasonal allergic rhinitis.
OBJECTIVES:	
Primary Objective To assess the safety and tolerability of B244 relative to vehicle in healthy volunteers during 14 days of treatment and up to 28 days of follow-up.
 
Secondary Objective(s)
 
  To evaluate the efficacy of B244 relative to vehicle in treating Total Nasal Symptom Score (TNSS) in subjects with seasonal allergic rhinitis evaluated in a nasal allergen challenge model as a prophylaxis therapy after 14 days of treatment.  To evaluate the safety and tolerability

	
of B244 relative to vehicle in subjects with allergic rhinitis after 14 days of treatment.
 
 To evaluate the efficacy of B244 relative to vehicle in treating individual nasal symptom scores in subjects with allergic rhinitis evaluated in a nasal allergen challenge model as a prophylaxis therapy after 14 days of treatment.
 
Exploratory Objective
 
 To test the hypothesis that B244 inhibits airway inflammation driven by nasal allergen challenge. The outcome measures will be changes in Peak Nasal Inspiratory Flow, nasal inflammation score using otoscope, intranasal nitric oxide levels and cytokine concentration from nasal cavity pre- and post- nasal allergen challenge in a prophylaxis treatment setting.

ENDPOINTS:	
Primary
 
Safety and tolerability will be assessed by reporting of AEs, physical examination and vital signs (blood pressure, heart rate, respiratory rate) during 14 days of treatment and up to 28 days of follow-up (Part 1).
 
Secondary
 
  Change in TNSS from baseline to 14 days of prophylaxis treatment.  Change in subjective nasal symptom scores of nasal congestion, rhinorrhea, nasal itching, and sneezing from baseline to 14 days of prophylaxis

	
treatment.
 
Nasal symptom-free response rate within each individual symptom scores and percentage of subjects with a 25% or 50% reduction in TNSS after 14 days of prophylaxis treatment.
 
 Safety and tolerability will be assessed in subjects with allergic rhinitis by reporting of AEs, physical examination and vital signs (blood pressure, heart rate, respiratory rate) during 14 days of treatment (Part 2).
 
Exploratory
 
 Change in Peak Nasal Inspiratory Flow (PNIF), nasal inflammation score using otoscope, intranasal nitric oxide levels, and cytokine concentration in nasal cavity and blood from baseline to 14 days of B244 application and during prophylaxis treatment setting.

STUDY DESIGN:	
This is a Prospective, Controlled, Double Blinded, Multi-Center, Randomized, 3 Arm, Parallel Assignment, Phase 1b/2a Study to assess the safety, tolerability, and preliminary efficacy of B244 delivered as an intranasal spray in healthy volunteers and subjects with seasonal allergic rhinitis. This will be a 2-part study. In Part 1, safety and tolerability will be evaluated during 14 days of study treatment twice-a-day followed by 4 weeks of follow-up in healthy volunteers. In Part 2, preliminary efficacy will be evaluated in subjects with a history of seasonal allergic rhinitis outside of the local pollen season.
 
Part 1 (safety and tolerability evaluation in healthy volunteers) will enroll 24 subjects. Up

	
to 12 subjects per dose cohort (n=8 active, n=4 vehicle) will be enrolled, with a target of 20 subjects completed (10 subjects per dose cohort; n=7 active, n=3 vehicle) assuming a 16.7% drop out rate.
 
Safety and tolerability will be assessed by reporting of AEs, physical examination and vital signs (blood pressure, heart rate, respiratory rate) during 14 days of treatment and up to 28 days of follow-up.
 
Subjects will be asked to report for a screening visit and if all inclusion/exclusion criteria are met, subjects will be asked to report for a baseline visit and randomization. Subjects will then be trained on the use of the nasal spray, and have their first dose of treatment on site. Subjects will remain onsite for observation for 1 hour post dosing. Subjects will then be dispensed study medication for 14 days of at home dosing. While at home, subjects will dose twice daily (am and pm), and record their dosing, any occurrence of an AE, and Total Nasal Symptom Score (TNSS) using a study diary. Subjects will be asked to visit the site at Day 14 (Week 2) and at follow-up visits at Day 21 (Week 3) and Day 42 (Week 6) for safety assessments and will additionally obtain Peak Nasal Inspiratory Flow (PNIF), intranasal fluid, intranasal nitric oxide (nNO) and nasal inflammation score.
 
During the 2 week safety phase (Part 1), a continuous Ambulatory Blood Pressure Monitoring (ABPM) device will monitor blood pressure of each subject for 24 hours at baseline and Day 14. ABPM would be worn for 24 hours prior to the baseline visit and

--	--

	
again for 24 hours prior to the Day 14 visit.
 
For Part 1, study will be paused for safety review LQWKHHYHQWWKDWMXEMHFWUHSRUWVD serious DGYHUVHHYHQWJUDGHMHYHUH DGYHUVHHYHQWVRUJUDGHPRGHUDWH adverse events considered possibly, probably, or definitely related to the investigational product. In addition, a 180 day follow up contact for collecting serious adverse events and new onset medical conditions will be provided.
 
An internal safety committee meeting will review the 2 week Part 1 safety data and, if there are no safety concerns, the study will proceed to Part 2 to evaluate preliminary efficacy in subjects with a history of seasonal allergic rhinitis (SAR)
 
Part 2 (preliminary efficacy evaluation in subjects with a history of SAR to ragweed pollen) will enroll 42 subjects. Up to 14 subjects per arm (1×10^9 cells/ml; 4×10^9 cells/ml or vehicle) will be enrolled, with a target of 12 subjects per arm for a total of 36 subjects completed, assuming a 10-15% drop-out rate.
 
Safety and tolerability will be assessed in subjects with allergic rhinitis by reporting of AEs, physical examination and vital signs (blood pressure, heart rate, respiratory rate) during 14 days of treatment.
 
A preliminary efficacy assessment will be performed in response to nasal allergen challenge (NAC) in a prophylaxis treatment setting.

--	---

	
Subjects will be asked to report for a screening visit (Visit 1) and if all inclusion/exclusion criteria are met, subjects will be asked to report for a NAC titration (ragweed pollen nasal allergen titration) visit to administer a single provocative challenge dose for each subject (Visit 2). Subjects will then return 14 days after the washout period for basic health checks and baseline assessments (intranasal fluid, TNSS, PNIF, intranasal nitric oxide, and have a nasal inflammation score) followed by confirmatory NAC (NAC#1) (Visit 3). During this time subjects will use a study diary to complete TNSS at -30 (30 minutes prior to NAC), 0 (baseline prior to NAC), 15, 30, 45, 60, 90, and 120 minutes. PNIF at -30, 0, 15, 30, 60, and 120 minutes will also be obtained. TNSS is the sum of four individual symptom scores (running nose, congestion, itchy nose, and sneezing) rated on a four point scale (0-3). Subjects are required to meet the minimum qualifying TNSS score of a change of 6/12 from their baseline score, on at least 2 diary cards. Subjects will also provide samples for intranasal fluid at 0, 20, and 60 minutes, measure intranasal nitric oxide (nNO) and have a nasal inflammation score assessed by the investigator using a nasal otoscope at 0 and 120 minutes, in addition to blood collection at 120 min for biomarkers. Subjects meeting the requirement will be randomized to one of the three treatment arms. Randomization will be 1:1:1 so that equal number of subjects will be treated in each arm of the study. Subjects will then be trained on the use of the nasal spray, and have their first dose of treatment on site (self-dosing). Subjects will remain onsite for observation for 1 hour post dosing. Subjects will then be dispensed study medication for 14

--	--

	
days of at home dosing. While at home, subjects will dose twice daily (am and pm), and record their dosing, and any occurrence of an AE and TNSS using a study diary.
 
Subjects will return to the clinic for the last dose following the 14 days of at home dosing for their final visit (Visit 4). During this time subjects will again have their baseline assessments and be exposed to ragweed pollen challenge (NAC#2), and will use a study diary to complete TNSS at -30, 0, 15, 30, 45, 60, 90, and 120 minutes and PNIF at -30, 0, 15, 30, 60, and 120 minutes. Prior to and 20 and 60 minutes after NAC #2, subjects will additionally provide samples for intranasal fluid, and have nNO measured and nasal inflammation score assessed by the investigator using a nasal otoscope at 0 and 120 min, in addition to blood collection at 120 min for biomarkers.
 
For Part 2, study will be paused for safety review using the same stopping criteria as in Part 1.
 
Rescue medications will not be allowed during the study.

STUDY POPULATION:	
Normal healthy volunteers and subjects with a history of seasonal allergic rhinitis to ragweed pollen are eligible for enrollment. Patients must be willing to refrain from using any treatments, investigational products, including herbal medicines while participating in this study.

MAIN INCLUSION/EXCLUSION CRITERIA:	
Inclusion Criteria
 
Males and Females, 18 to 65 years of age (committed to consistent use of an acceptable method of birth control).
 
 In good general health as determined by

[figure not shown]
	
a thorough medical history and physical examination, and vital signs.
 
 Nonsmoker or ex-smoker (stopped >1 year prior to study entry). Subjects willing and able to provide written informed consent. Is willing and able to comply with the requirements of the protocol and must be available for the full duration of the study. For Part 1, subjects asymptomatic from any seasonal or perennial allergens. For Part 1, elevated systolic blood pressure greater than 120 but less than 160 and never been on antihypertensive medications or have been off any hypertensive treatment for a period of 12 weeks or longer. For Part 2, subjects with a well-documented history of seasonal allergic rhinitis (specifically ragweed pollen) with documentation of sensitivity by positive skin testing and/or IgE testing to the relevant allergens 12 months prior to enrollment that correlate with clinical history. For Part 2, a ragweed positive skin prick test with a wheal diameter at least 5 mm larger than the negative control and/or a ragweed specific IgE greater or equal to 0.7 kU/L. For Part 2, subjects with confounding allergies, or sensitization to cat epithelia, dog epithelia, Dermatophagooides farinae, or Dermatophagooides pteronyssinus or prevalent and relevant seasonal allergens as per the skin prick test may be included if sensitization is not clinically relevant (ie. subject is non-
--	--

[figure not shown]
	
symptomatic and/or can avoid the allergen during the study) at the discretion of the Investigator.
 
  For Part 2, subjects with a baseline TNSS  at Visit 3 and a minimum qualifying TNSS score of a change of 6/12 from their baseline score after NAC #1 on at least 2 diary cards.  For Part 2, subjects' average post diluents nasal congestion score must be  at admission for each study visit. 
Exclusion Criteria
 
Patients who meet any of these criteria are not eligible for enrollment as study participants:
 
  Pregnancy or breast-feeding  Female of childbearing potential not using adequate contraceptive measures  Smoking within the past year or during the protocol.  Systemic corticosteroid or other immunosuppressive medications use in the previous three months or during the protocol.  Intranasal corticosteroid use in the previous month or during the protocol.  Intranasal antihistamine or cromolyn use in the previous week or during the study.  Allergen immunotherapy during previous 12 months or during the protocol.  Omalizumab use in previous 12 months or during the protocol.  Systemic antihistamine or leukotriene modifying medication use in the previous week or during the protocol.  Use of antibiotics, NSAIDS, antihypertensives, beta-blockers,
--	--

	
photosensitizing medications, or vitamin D supplements during study. Antihypertensive and beta-blocker exclusion applies to Part 1 only.
 
  Use of any intranasally administered over-the-counter product or nasal irrigation (e.g., neti pot) during study.  Inability to give informed consent.  Persistent asthma or any medical condition that in the opinion of the investigator may compromise the subject's ability to safely participate in the study.  Subjects with any significant clinical abnormalities which may interfere with study participation.  Prior use of AO+ Mist  Subjects with immunodeficiencies, nasal lesions, nasal polyps, or sinus infections.  Use of an investigational drug within 30 days before screening Visit 1
DOSE REGIMEN:	
In Part 1, after screening and recruitment, participants will be randomized to one of the following arms of the study for 2 weeks of treatment and 4 weeks of follow-up:
 
 1. B244 (140ul per nostril; OD 0.5; 1×10^9 cells/ml) twice-a-day for 14 days, 2. B244 (140ul per nostril; OD 2.0; 4×10^9 cells/ml) twice-a-day for 14 days 3. Vehicle (140ul per nostril) twice-a-day for 14 days 
In Part 2, subjects with a history of SAR to ragweed pollen will be enrolled to one of the following arms:
 
 1. B244 (140ul per nostril; OD 0.5; 1×10^9

	
cells/ml) twice-a-day for 14 days, 2. B244 (140ul per nostril; OD 2.0; 4×10^9 cells/ml) twice-a-day for 14 days, 3. Vehicle (140ul per nostril) twice-a-day for 14 days,
 
Subjects will undergo nasal allergen challenge, followed by one-time treatment in clinic on Day 0, followed by twice-a-day in-home treatment for 14 days, followed by one additional treatment in clinic on Day 14 prior to second nasal allergen challenge.

ASSESSMENT SCHEDULE:	
In Part 1, study assessments will occur at Baseline and Week 2 (Day 14) visit. Follow-up visit will be at Week 3 (Day 21) and Week 6 (Day 42) after treatment to perform safety assessments and clinical examination of the nasal mucosa, sinuses, and upper airway.
 
In Part 2, study assessments will occur at NAC titration visit (Day 0), NAC#1 visit (Day 14) and NAC#2 visit (Day 28). Preliminary efficacy assessments will be after nasal allergen challenge in a prophylaxis treatment setting.

STATISTICAL CONSIDERATIONS:	Intent to treat analysis
INVESTIGATIONAL DRUG AND PLACEBO:	
Investigational drug refers to B244.
 
Investigational Product/treatment refers to either B244 or Vehicle.

PLANNED DURATION PER SUBJECT:	Up to 9 weeks
DURATION OF STUDY:	
First subject first visit: Sep 2017
 
Study readout: Mar 2018

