2.1 Background

Allergic rhinitis (AR) is an upper airway inflammatory disease, characterized by symptoms of rhinorrhea, sneezing, and nasal congestion. Although AR is often considered a benign condition, it greatly impacts the quality of life of affected individuals, with economic costs estimated at \$5.3 billion per year in the USA (1,2). World-wide prevalence of AR is estimated at 9% to 42% (3,4). A variety of treatment approaches exist, including anti-histamines, corticosteroids, and immunotherapies, but have associated side effects and variable responses that warrant alternative options that exhibit improved safety and efficacy profiles. None of the current anti-allergic and anti-inflammatory interventions is designed to address a microbiome based approach to restore colonization of a human commensal bacteria to the nasal microbiome to regulate its anti-inflammatory and anti-infective properties. Intranasal administration of ammonia oxidizing bacteria maybe beneficial for the treatment of a variety of local and systemic indications through its anti-inflammatory and anti-infective properties. The objective of this study is to evaluate the safety of intranasally delivered ammonia oxidizing bacteria (AOB) in healthy volunteers and subsequently to evaluate preliminary efficacy of AOB as a prophylaxis treatment in response to a ragweed pollen nasal allergen challenge (NAC) in subjects with a history of seasonal allergic rhinitis (SAR).

Ammonia oxidizing bacteria are essential for the initial step in environmental nitrification processes, specifically the oxidation of ammonia (NH_3) to nitrite (NO_2^-). *Nitrosomonas* are Gram-negative chemolithoautotrophic betaproteobacteria that obtain energy solely from NH_3 oxidation, while fixing CO_2 for their carbon needs (5). Oxidation of NH_3 proceeds in two steps (

[Figure 1](#)) leading to sequential generation of hydroxylamine (NH_2OH) and NO_2^- that require two enzyme complexes: the membrane-bound ammonia monooxygenase (AMO) comprised of subunits AmoA, AmoB and AmoC; and the periplasmic NH_2OH oxidoreductase (HAO). In addition to high NO_2^- levels, NH_3 oxidation leads to nitric oxide (NO) and N_2O production through two independent pathways downstream of NH_2OH production: nitrifier denitrification and NH_2OH oxidation (6).

Figure 1 Nitrifier Denitrification Pathway

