Currently, *Nitrosomonas eutropha* D23 in buffer at a concentration of 1x10⁹ cells/mL is available as a cosmetic product for topical application of a natural source of AOB and NO/NO₂ to improve the appearance of human skin. AOBiome plans to study *Nitrosomonas eutropha* D23 diluted in storage solution (50 mM Na₂HPO₄ and 2 mM MgCl₂, pH 7.6) at defined doses to be provided as an intranasal spray (B244) for therapeutic applications.

B244 is being developed under IND #16487 as a 'live topical' to provide a natural source of AOB and NO/NO₂ to the human skin. Under IND #16487, a phase 1b/2a clinical trial was completed in 2016 where 36 participants with clinical diagnosis of facial acne vulgaris were randomized to receive ascending doses of investigational product (IP) over 14 days. Safety analyses have been completed and there have been no attributable drug related SAEs reported. In addition, a phase 2b/3 clinical trial in 372 patients with clinical diagnosis of facial acne is

currently ongoing. To date, there have been no attributable drug related SAEs reported in this trial.

The proposed clinical study is designed to evaluate the safety of intranasally delivered AOB in healthy volunteers and subsequently to evaluate preliminary efficacy of AOB as a prophylaxis treatment in response to a ragweed pollen nasal allergen challenge in subjects with a history of seasonal allergic rhinitis.

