8.15 Handling of Investigational Product

Subjects will receive one 30 ml bottle for each Part of the study. Each bottle will be used for 14 days and brought to study appointment. The bottle may be placed on the counter to be used during the treatment period.

Subjects will be asked not to subject the treatment kit to conditions which are unnatural or harmful to the product, such as excessive heat (temperatures over 77°F (25°C) and freezing temperatures (at 0°C)). Subjects may travel with their study medication but should not leave it in the hot car, outside in the cold temperatures etc. Subjects will also be asked not to tamper or cause damage to IP.

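### Prior AO+ Mist use is excluded without time limit but prior B244 use only for 30 days, and nothing expressly keeps Part 1 or acne-trial participants out of Part 2

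*Protocol*

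**What the plan says.** The synopsis (Main Inclusion/Exclusion Criteria) and Protocol 6.4 carry the same two lines. One excludes "Prior use of AO+ Mist", with no time limit. The other excludes "Use of an investigational drug within 30 days before screening Visit 1". The synopsis also states: "Investigational drug refers to B244". On that definition the 30-day line is the B244 limit. If it is read as covering any investigational drug, it is still the only line that reaches earlier B244 use.

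Protocol 2.1 describes a *Nitrosomonas eutropha* D23 product that "is available as a cosmetic product for topical application of a natural source of AOB". The protocol never names that product as AO+ Mist; the identity is a reasonable inference and no more. The same section reports two B244 acne trials: one completed in 2016 with 36 participants, and "a phase 2b/3 clinical trial in 372 patients with clinical diagnosis of facial acne", still running when the protocol was written. It presents the treatment idea as one meant to "restore colonization of a human commensal bacteria to the nasal microbiome".

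On allergy, Protocol 6.3 asks "For Part 1, subjects asymptomatic from any seasonal or perennial allergens", whereas Part 2 needs a documented history of ragweed rhinitis with a positive skin test or IgE. Protocol 8.15 says: "Subjects will receive one 30 ml bottle for each Part of the study".

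**The concern.** One product is barred for life, while the study drug is barred for 30 days, and no reason is given for the difference. Nothing in the criteria then stops a person who received B244 in an acne trial, or possibly in Part 1, from being randomised in Part 2.

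Two things are at stake. First, the rationale involves colonisation by a live organism, no section gives a clearance time, and PCR for B244 is optional (Protocol 11.11) and not an entry check. Part 2 could therefore compare arms in which some subjects are not new to the treatment, and SAP 2.5.1 has no term, subgroup or sensitivity analysis for prior exposure. Second, Part 1 safety is the primary objective and has a 180-day follow-up contact for serious events and new conditions (Protocol 5 and 12.2). A second course and further allergen challenges inside that period would make later events hard to attribute.

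**Working it through.** There is no planned figure to reproduce: SAP 2.7 says the sample size has no statistical basis. The check is a comparison of criteria, a day count, and the algebra of the planned analysis.

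**Routes into Part 2**
- *Acne trials.* A participant whose last use was more than 30 days before screening, and who meets the ragweed criteria, meets no exclusion on account of that use. The route is open.
- *Part 1.* Being asymptomatic is not the same as having no allergy history, so someone with ragweed rhinitis who is out of season could meet the Part 1 allergy criterion and later those of Part 2. The route is not closed.

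**Day count for a Part 1 subject (last dose Day 14)**
- Check against Protocol 12.2: 21 − 14 = 7 and 42 − 14 = 28 days after the last dose, as stated there.
- The 30-day line is met from Day 14 + 30 = 44, which is 44 − 42 = 2 days after the final Part 1 visit. It adds almost nothing to the Part 1 schedule.
- With Part 2 screening on Day 44 and the nominal schedule, titration falls on 44 + 1 = Day 45, NAC #1 and the first new dose on 45 + 14 = Day 59, and NAC #2 on 45 + 28 = Day 73.
- A 180-day contact counted from the last Part 1 visit falls on 42 + 180 = Day 222. All of the above lies before it.

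**Effect on the Part 2 comparison**

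SAP 2.5.1 summarises the change from Visit 3 to Visit 4 and tests Visit 4 by ANCOVA with the Visit 3 value as covariate. Let *d* be the reduction in challenge TNSS from a 14-day course. Let *f* be the share of an earlier effect still present at both visits. Let *b* be the ANCOVA slope (*b* = 1 is the change score), *n* the completers per arm, and *k*V and *k*A the previously exposed completers in the vehicle arm and in one active arm. Assume that a new course brings a subject to *d* and no further.
- Exposed vehicle subject: Visit 3 and Visit 4 are both lower by *fd*, so the adjusted value is lower by (1 − *b*)*fd*.
- Exposed active subject: Visit 3 is lower by *fd* and Visit 4 by *d*, so the adjusted value is lower by *d* − *bfd*.
- Contrast = *d* × {1 − *f* [(1 − *b*)*k*V + *b* *k*A] / *n*}.

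On the change score (*b* = 1) this is *d*(1 − *f k*A/*n*): the vehicle-arm term vanishes and the whole loss comes from the active arm. With *b* between 0 and 1 both arms contribute. If *f* = 0 there is no loss.

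The ceiling assumption matters. If earlier and new effects simply added, the contrast would be *d* + (1 − *b*)*fd*(*k*A − *k*V)/*n*, which equals *d* when exposure is balanced, as randomisation makes it in expectation.

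The documents give none of *f*, *b*, *k*V or *k*A. The algebra therefore shows direction and route, not size.

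**The case against.** The strongest case against has four parts.

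- **The Part 1 route runs against the design.** The plan names two different populations (Protocol 6.1), and Part 1 also requires systolic pressure above 120 and below 160. The stated maximum of nine weeks per subject is filled by Part 1 alone: (21 + 42)/7 = 9.0 weeks. Part 2 takes (21 + 28)/7 = 7.0, and both would take 16.0. The bottle sentence in 8.15 is best read as shorthand for 8.7, which describes one bottle at the relevant visit of each part. With 16 of 24 Part 1 subjects on B244 and one third of Part 2 on vehicle, one expected B244-exposed vehicle subject would need 1/(2/3 × 1/3) = 4.5 crossovers, about 19% of Part 1. This stands and makes the route narrow, but the duration line is not an eligibility rule.
- **The challenge screens subjects before randomisation.** Protocol 11.7 requires a qualifying response at titration, then a TNSS change of 6 out of 12 on at least two diary cards at NAC #1. A subject strongly protected by earlier B244 would tend to fail. This stands and limits *f* among those randomised.
- **The 30-day line may be deliberate for B244**, given the synopsis definition, and there are no persistence data to show it is too short. That is fair, but the documents do not explain the difference from AO+ Mist.
- **Part 2 efficacy is preliminary and secondary.** This limits the weight of the point.

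Two stronger readings are tempting. A reader might infer that each previously exposed vehicle subject costs 1/14 to 1/12 (7 to 8%) of the contrast. That treats Visit 4 as if Visit 3 were ignored (*b* = 0) with full persistence, and the planned analysis does not do this. A reader might also infer that a subject in both parts breaks an independence assumption. SAP 2.1 presents the parts separately, and no planned analysis pools them.

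**Conclusion.** The eligibility gap is real, in both the synopsis and 6.4. B244 recipients from the acne trials can enter Part 2 on the text as written, and Part 1 subjects are not expressly barred.

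The harm cannot be sized, and it may be nil. It needs at least one such subject to be enrolled and, for efficacy, an earlier effect that outlasts the interval and does not simply add to the new course. Under those assumptions the bias is towards no difference, acts partly or mainly through previously exposed active-arm subjects, and is limited by the NAC #1 qualifying response. The safety point needs no persistence assumption: a Part 1 subject who re-enters within 180 days confounds the Part 1 follow-up. This is a cheap improvement, not a flaw that undermines the trial.

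**What to change.** Reconcile the two criteria. In the synopsis and in Protocol 6.4, extend the AO+ Mist line so that it also covers prior use of B244, including participation in Part 1 of this study or in any other B244 trial. Wording it by participation avoids having to learn a blinded allocation. Check it at Visit 1.

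If re-entry is in fact intended, the protocol should say so, and the SAP should state how prior exposure will be handled.

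The cost is one eligibility line in two places and a very slightly smaller recruitment pool.
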